9.4.1 Ongoing Pregnancy Rate

The ongoing pregnancy rate will be calculated and tabulated for the fresh cycle and for each cryopreserved cycle sequentially (overall and within programmed and natural cryopreserved cycles separately), and for cryopreserved cycles cumulatively based on both the total number of subjects in the treatment group and the total number of subjects who started the respective cycle.

Note that, as a result of late pregnancy loss (after confirmation of ongoing pregnancy), a subject is allowed to come back for another transfer within one year from the start of stimulation, as long as there is at least one blastocyst remaining. The eCRF will be kept open for the subject to capture potentially further cryopreserved cycle information up to one year from the start of stimulation unless the subject withdraws consent or when all her blastocysts are exhausted. Therefore, a subject may achieve more than one ongoing pregnancy within two different cycles in the trial, but for cumulative ongoing pregnancy rates, a subject can only be counted once in the numerator.

Analyses similar to that used for the primary endpoint will be applied for the fresh cycle, and for cryopreserved cycles as applicable i.e. where there is at least one subject who started the respective cycle in both treatment groups and will be applied to both the mITT and PP analysis sets.

For subjects with an ongoing pregnancy, the number of intrauterine viable fetuses will be tabulated overall and by ongoing pregnancy in sequential order.

9.4.2 Time to Ongoing Pregnancy

For subjects who achieve ongoing pregnancy following a fresh or cryopreserved transfer, time to the first ongoing pregnancy across the fresh and cryopreserved cycles will be calculated as the number of days from the start of controlled ovarian stimulation to the first visit confirming ongoing pregnancy, as well as the number of cycles until ongoing pregnancy is achieved. The number of days will be presented in two ways: total number of days and number of days within cycles (i.e. excluding the periods between the end-of-cycle visit and the next cycle initiation). Descriptive statistics will be presented by treatment group, and will be applied to both the mITT and PP analysis sets.

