9.7.3.2 Time to Ongoing Pregnancy

For subjects who achieve ongoing pregnancy following a fresh or cryopreserved transfer, time to ongoing pregnancy across the fresh and cryopreserved cycles will be calculated as the number of days from the start of controlled ovarian stimulation to the visit confirming ongoing pregnancy, as well as the number of cycles until ongoing pregnancy is achieved. Descriptive statistics will be presented by treatment group, and will be applied to both the mITT and PP analysis sets.

Trial Code: 000002 Date: 25 Apr 2018 E-Study Protocol-22377; Ver. 1.0

> Supersedes: None Page 131 of 159

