2.2 Endpoints

Primary Endpoint

• Cumulative ongoing pregnancy rate (at least one intrauterine viable fetus 8-9 weeks after transfer) after the fresh cycle and cryopreserved cycles initiated within 12 months from the start of controlled ovarian stimulation

Secondary Endpoints

- Ongoing pregnancy rate (at least one intrauterine viable fetus 8-9 weeks after transfer) in the fresh cycle and in the cryopreserved cycles
- Time from start of controlled ovarian stimulation to ongoing pregnancy across the fresh and cryopreserved cycles, including duration and number of cycles before achieving ongoing pregnancy
- Ongoing implantation rate (number of intrauterine viable fetuses 8-9 weeks after transfer divided by number of blastocysts transferred) in the fresh cycle, the cryopreserved cycles and cumulatively
- Clinical pregnancy rate (at least one gestational sac 5-6 weeks after transfer) in the fresh cycle, the cryopreserved cycles and cumulatively
- Vital pregnancy rate (at least one intrauterine gestational sac with fetal heart beat 5-6 weeks after transfer) in the fresh cycle, the cryopreserved cycles and cumulatively
- Implantation rate (number of gestational sacs 5-6 weeks after transfer divided by number of blastocysts transferred) in the fresh cycle, the cryopreserved cycles and cumulatively
- Positive βhCG rate (positive serum βhCG test 10-14 days after transfer) in the fresh cycle, the cryopreserved cycles and cumulatively
- Proportion of subjects in the fresh cycle with triggering of final follicular maturation (with hCG, with GnRH agonist, and in total), cycle cancellation and transfer cancellation
- Number and size of follicles on stimulation day 5 and end-of-stimulation
- Number of oocytes retrieved and proportion of subjects with <4, 4-7, 8-14, 15-19 and ≥20 oocytes retrieved
- Number and percentage of metaphase II oocytes (only applicable for those inseminated using ICSI), number of fertilized oocytes, fertilization rate as well as number and quality of blastocysts on day 5 after oocyte retrieval
- Endometrial thickness and echogenicity pattern on stimulation day 5 and end-of-stimulation
- Oocyte utilization rate (number of blastocysts transferred or cryopreserved divided by the number of oocytes retrieved) and oocyte efficiency index (cumulative number of ongoing pregnancies per oocyte retrieved)
- Number and percentage of blastocysts surviving cryopreservation and number and percentage of blastocysts with re-expansion after cryopreservation

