3.2 Determination of Sample Size

The proposed sample size of 550 (FE 999049:placebo = 500:50) can adequately address both the efficacy and safety objectives of the trial:

- The cumulative ongoing pregnancy rate in the FE 999049-treated subjects aged 35-42 years is estimated to be approximately 30% according to results from clinical trials conducted in the U.S.¹ By comparison, the pregnancy rate in the placebo arm is expected not to exceed 3%, the monthly spontaneous pregnancy rate in infertile women.² Therefore, the proposed sample size of 550 (FE 999049:placebo=500:50) will provide at least 99% power for the primary efficacy comparison. Based on the estimated cumulative ongoing pregnancy rate, the cumulative live birth rate from the fresh and/or cryopreserved cycles is estimated to be approximately 27%, resulting in a power for the comparison of the cumulative live birth rate to be at least 99%.
- A key pharmacodynamic parameter in subjects aged 35-42 years is cycle cancellation due to poor follicular development, which may occur in approximately 5% of the population exposed to gonadotropins.
- The safety and tolerability of daily rFSH preparations as part of an ART treatment cycle have been well documented for the population studied in previous clinical trials.^{3,4} OHSS was reported to occur in 1.7% to 3.7% of the subjects, with moderate/severe OHSS occurring in 1.4% to 2.2% of the subjects. Other adverse events were pelvic pain, pelvic discomfort and headache, with those assessed to be related to trial treatments reported in 1.5% to 7.1% of the subjects.

Table 1 shows that the planned sample size of 500 subjects exposed to FE 999049 provides a high probability to detect a rare adverse event or safety signal occurring in 0.5% or more subjects.

Incidence rate of rare event	Chance of detecting at least 1 event
0.5%	91.8%
0.6%	95.1%
1%	99.3%

Table 1Probabilities to Detect at Least One Rare Event

Table 2 presents the margin width estimates of the 95% confidence intervals for a range of adverse event rates with the planned sample size.

Adverse event rate	Margin of error width estimate
5%	1.9%
10%	2.6%
15%	3.1%
20%	3.5%

Table 2Estimated Margin Widths of 95% Confidence Intervals

4 Subject Disposition

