11.1.4 Time to Live Birth of a Singleton Born at Term

For subjects who achieve live birth of a singleton born at term, time to live birth of a singleton born at term across the fresh and cryopreserved cycles will be calculated as the number of days from the start of controlled ovarian stimulation to delivery, as well as the number of cycles until delivery. The number of days will be presented in two ways: total number of days and number of days within cycles

(i.e. excluding the periods between the end-of-cycle visit and the next cycle initiation). sDescriptive statistics will be presented by treatment group.

The time to live birth of a singleton born at term will also be summarized by whether each subject had any cycles leading to birth that occurred during or after the COVID-19 pandemic trial hold. Descriptive statistics will be presented by treatment group.

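### Time to ongoing pregnancy and to term singleton live birth are summarised only in women who succeed, so a group with fewer late successes shows a shorter mean time

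*SAP*

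**What the plan says.** The secondary endpoint in SAP 2.2 is "Time from start of controlled ovarian stimulation to ongoing pregnancy across the fresh and cryopreserved cycles", expressed as duration and as number of cycles. As listed, it concerns every woman who starts stimulation.

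The analysis sections narrow it. Protocol 9.7.3.2 reads "For subjects who achieve ongoing pregnancy following a fresh or cryopreserved transfer, time to ongoing pregnancy across the fresh and cryopreserved cycles", and SAP 9.4.2 keeps the restriction, adding that the first ongoing pregnancy counts: "For subjects who achieve ongoing pregnancy following a fresh or cryopreserved transfer, time to the first ongoing pregnancy across the fresh and cryopreserved cycles". The output is specified as "Descriptive statistics will be presented by treatment group, and will be applied to both the mITT and PP analysis sets". SAP 9.4.2 reports duration on two scales, "total number of days and number of days within cycles", the second leaving out gaps between cycles. The post-trial counterpart, SAP 11.1.4, begins "For subjects who achieve live birth of a singleton born at term, time to live birth of a singleton born at term", as does protocol 9.10.1.4 in substance.

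For these endpoints neither document gives a censoring rule, a cumulative-incidence or Kaplan-Meier display, or any role for women who do not reach the event. Naming the mITT and PP sets does not change this, because each set is first cut to its successes.

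**The concern.** A mean or median among achievers answers how long success took in those who succeeded. It does not describe time from starting stimulation, because women who never conceive contribute nothing. The summary depends on the mix of early (fresh-cycle) and late (cryopreserved-cycle) successes. A group that loses late successes has a lower pregnancy rate and a shorter mean time together, so the display can move opposite to efficacy.

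The hold adds an ambiguity. SAP 9.3.2 defines both a 12-calendar-month window (primary analysis) and a 12-study-month window (sensitivity analysis for affected women). SAP 9.4.2 does not say which governs the time endpoint, and the two can push the mean in opposite directions.

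At stake is the meaning of one listed secondary and one post-trial endpoint. No formal test is involved.

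**Working it through.** **Inputs from the documents.** SAP 3.2: "The proposed sample size of 550 (FE 999049:placebo = 500:50"), FE 999049 rate about 30%, placebo rate not above 3%. The plan states no figure for time to pregnancy. Its related figure, power of at least 99% for 30% against 3%, reproduces (0.999995; pooled two-sided z test, alpha 0.05).

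**Who enters the summary.**
- FE 999049: 500 × 0.30 = 150 women in, 350 (70%) out.
- Placebo: 50 × 0.03 = 1.5 expected. P(none) = 0.97^50 = 21.8%; P(at most one) = 55.5%.

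**Direction.** With n_e early successes at time t_e and n_l late ones at t_l > t_e, the mean among achievers is (n_e·t_e + n_l·t_l)/(n_e + n_l). For fixed n_e it falls whenever n_l falls.

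**Size (assumptions).** The documents give no timing split. Assume confirmation at day 80 (fresh), 200 (first cryopreserved cycle) and 320 (second). Day 80 fits the schedule: an assumed 10 stimulation days + 1.5 to retrieval + 5 to transfer + 56 to 69 gives 72.5 to 85.5. Take 500 women per group and identical fresh-cycle results.

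| Group | Pregnancies at day 80/200/320 | Rate | Mean among achievers | Cumulative incidence at day 80/200/320 |
|---|---|---|---|---|
| A | 75/50/25 | 30.0% | 24,000/150 = 160.0 days | 15/25/30% |
| B | 75/25/12 | 22.4% | 14,840/112 = 132.5 days | 15/20/22.4% |
| C | 75/0/0 | 15.0% | 6,000/75 = 80.0 days | 15/15/15% |

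The group with the fewest pregnancies looks fastest; cumulative incidence in all women orders the groups correctly. Mean pregnancy-free days to day 365 in all women agree with that order: (24,000 + 350 × 365)/500 = 303.5 for A, (14,840 + 388 × 365)/500 = 312.9 for B.

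**Range over the split.** Lose half the late successes, with fresh/first/second shares as shown:
- 30/45/25%: mean 194.0 to 167.7 days, rate 30% to 19.5%.
- 50/33/17%: 160.4 to 133.6 days, rate 30% to 22.5%.
- 70/20/10%: 128.0 to 108.2 days, rate 30% to 25.5%.

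**A milder case.** With 90 pregnancies at day 80 and 60 at day 220, the mean is 20,400/150 = 136 days. Removing 15 late ones gives 17,100/135 = 126.7 days, and the rate falls from 30% to 27%. The median stays at 80.

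**Hold (assumed cohort of 250).** Unaffected, 38/25/12 gives 11,880/75 = 158.4 days and a 30% rate.
- Late successes lost under 12 calendar months (38/12/0): 5,440/50 = 108.8 days, rate 20%.
- All 37 late successes delayed by H days but counted under 12 study months: 158.4 + H × 37/75, so 173.2, 188.0 and 202.8 days for H = 30, 60 and 90, rate still 30%.

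**The case against.** The strongest reply is that little is hidden. SAP 9.4.1 reports ongoing pregnancy rates for the fresh cycle, each cryopreserved cycle and cryopreserved cycles cumulatively, with all subjects in the arm as one denominator. SAP 9.3.2 gives all-mITT rates for cycles initiated within 6 calendar, 12 calendar and 12 study months. SAP 9.2 requires n and quartiles beside the mean, so a falling n is visible. The restriction to achievers is openly stated, and no display can give useful placebo timing from one or two pregnancies. This stands, and it is why the point is minor. However, those rates are indexed by cycle or by initiation window. None gives the listed quantity, time from start of stimulation to confirmation, in all women.

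A reader might also infer that the hold makes the affected women look faster. The documents do not support a direction. Protocol Amendment 01 extends the cryopreserved-cycle timelines and lets initiated cycles continue. SAP 9.3.2 allows affected women 12 study months, so late successes may be delayed rather than lost. The within-cycle day count also removes a hold falling between cycles. SAP 9.4 and 11.1.4 plan breakdowns by hold period, and SAP 9.4 expects few cycles during or after it. What remains is the unstated window, and the fact that breakdowns of started cycles, or of achievers, cannot show women who never started one.

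The size also rests on assumed splits. In the milder case only the mean moves, by about 9 days.

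**Conclusion.** The concern holds as a minor point about two descriptive endpoints. Restricting the summary to achievers conditions on the outcome; that mean times shorten when late successes are lost and early ones are unchanged follows from arithmetic alone. The size is illustrative: under assumed days 80/200/320, with 30% to 70% of successes in the fresh cycle, losing half the late successes shortens the mean by about 20 to 27 days. The median may not move.

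The effect of the hold is indeterminate until the window is stated. It would be wrong to infer that the trial's efficacy conclusion is at risk: neither time endpoint is in the testing hierarchy, and the primary endpoint keeps all mITT women in the denominator.

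**What to change.** In SAP 9.4.2 and 11.1.4, make the main display the cumulative incidence of the first event from start of stimulation, in all mITT women by arm.

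- **Ongoing pregnancy:** count cycles initiated within 12 calendar months, as in the primary analysis. Keep non-achievers, including women whose blastocysts are exhausted, event-free in the denominator. Report percentages at fixed times that reach the 8-9 week confirmation visit of the last eligible cycle. On the protocol's windows a programmed cycle can take about 12 + 7 + 5 + 5 + 69 = 98 days from initiation to that visit, so 3, 6, 9, 12 and 16 months would serve. With missing outcomes counted as negative, the last point should equal the primary rate, which is a useful check.
- **Live birth:** use times that extend to delivery.
- **Hold:** state the window in 9.4.2. Repeat the display under 12 study months as a sensitivity display, counting post-hold pregnancies. If a censored version is shown, censor at the hold only women with blastocysts remaining, no cycle under way and no later cycle within the window. Censoring every affected woman would discard post-hold outcomes that SAP 9.2.2 treats as observed, and censoring women with no blastocysts left would inflate the incidence.
- **Existing summary:** keep it as a supplement labelled conditional on success.

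The cost is one extra table and figure per endpoint, from dates, blastocyst counts and cycle status already collected. SAP section 14 already lists added displays for both endpoints.

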9.4.3 Ongoing Implantation Rate

The ongoing implantation rate will be calculated for the fresh cycle, for each cryopreserved cycle sequentially (overall and within programmed and natural cycles separately), cumulatively for the cryopreserved cycles, and cumulatively across the fresh and cryopreserved cycles for subjects with at least one transferred blastocyst in the applicable cycles.

For subjects where the number of viable fetuses 8-9 weeks after transfer is greater than the number of blastocysts transferred, the number of viable fetuses will be set to the number of blastocyst transferred in the analysis. Descriptive statistics will be presented by treatment group and the two treatment groups will be compared using the nonparametric Wilcoxon rank-sum test as applicable. The analyses will be applied to both the mITT and PP analysis sets.

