9.2 Analysis and Presentation of Primary and Secondary Efficacy Endpoints

Summary tables and treatment comparisons for the primary endpoint will be presented for both the mITT and PP analysis sets. In case that the mITT and ITT analysis sets are not identical (i.e. at least one subject is randomized but not exposed) the summary tables and treatment comparisons will also be presented for the ITT analysis set. As applicable for the secondary endpoints, summary tables and treatment comparisons may be presented for the mITT and PP analysis sets.

All tabulations will be presented by treatment group. Continuous variables will be presented with number of subjects, mean, standard deviation, median, inter-quartile range, minimum, and maximum. Categorical variables will be presented with number and percentage of subjects within each specific category.

All statistical tests will be performed using a two-sided test at a 5% significance level. Treatment differences will (where appropriate) be presented with 95% confidence intervals and p-values corresponding to the statistical test of the hypothesis of 'equal effect' against the alternative of 'different effect'.

Visual displays will be produced as appropriate. All primary and secondary efficacy endpoints will be listed. Listings will only be produced for the mITT.

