9.3 Primary Endpoint

The primary endpoint will be determined as soon as the subject has achieved an ongoing pregnancy, or when all cryopreserved blastocysts have been exhausted, or after assessment of ongoing pregnancy status in cryopreserved cycles initiated within 12 months from the start of controlled ovarian stimulation.

The superiority hypotheses to be tested for the primary endpoint are:

H₀: $\pi_{\text{FE 999049}} - \pi_{\text{Placebo}} \leq 0$ against the alternative H_A: $\pi_{\text{FE 999049}} - \pi_{\text{Placebo}} > 0$,

where $\pi_{FE 999049}$ and $\pi_{Placebo}$ denote the cumulative ongoing pregnancy rate after the fresh cycle and cryopreserved cycles in subjects aged 35-42 years treated with FE 999049 or placebo, respectively.

Ferring Pharmaceuticals

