9.4.6 Implantation Rate

The implantation rate will be calculated and analyzed in a similar manner as ongoing implantation rate and will be applied to both the mITT and PP analysis sets.

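### SAP 9.4.3 and 9.4.6 point to one cumulative implantation ratio per woman; because transfers normally stop at success, its mean overstates fetuses per blastocyst transferred and its Wilcoxon test can pick up blastocyst supply

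*SAP*

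**What the plan says.** SAP 2.2 defines the ongoing implantation rate as "number of intrauterine viable fetuses 8-9 weeks after transfer divided by number of blastocysts transferred", to be given for the fresh cycle, the cryopreserved cycles and cumulatively. It does not say whether the division is done once per arm or once per woman.

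SAP 9.4.3 restricts the overall cumulative row, giving the rate "cumulatively across the fresh and cryopreserved cycles for subjects with at least one transferred blastocyst in the applicable cycles". When a subject has more fetuses than blastocysts, "the number of viable fetuses will be set to the number of blastocyst transferred in the analysis". On the comparison it says that "the two treatment groups will be compared using the nonparametric Wilcoxon rank-sum test as applicable". Protocol 9.7.3.3 has the same rules. The general rule in SAP 9.2 is that "Continuous variables will be presented with number of subjects, mean, standard deviation, median, inter-quartile range, minimum, and maximum".

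For the second endpoint, SAP 9.4.6 states: "The implantation rate will be calculated and analyzed in a similar manner as ongoing implantation rate".

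On stopping, SAP 9.3 says: "The primary endpoint will be determined as soon as the subject has achieved an ongoing pregnancy". It then lists exhaustion of blastocysts and the 12-month limit. SAP 9.4.1 describes return for a further transfer after an ongoing pregnancy only when that pregnancy is later lost.

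**The concern.** A subject-level population, a subject-level cap and a rank test that needs one value per subject all point to a ratio for each woman. For a single transfer cycle this raises no difficulty of the kind described here.

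Over repeated transfers the denominator depends on the outcome. A woman who conceives at her first single transfer scores 1/1 and stops. One who conceives at her third scores 1/3. The mean of such scores is not the quantity defined in SAP 2.2 when that definition is read as fetuses per blastocyst.

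Two stated secondary endpoints are affected: cumulative ongoing implantation and cumulative implantation. The cumulative rows will stand beside single-cycle rows that lack this feature. A higher cumulative figure could then be taken for better performance of cryopreserved blastocysts. Stimulation is meant to increase the number of follicles and so of embryos, which means that the arms may well differ in blastocyst supply. The rank test could report that difference as one in implantation.

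**Working it through.** The plan gives no expected cumulative implantation rate, so there is no figure to reproduce.

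**Inputs.**
- Chance per blastocyst p = 0.31. Protocol 1.1 reports an ongoing implantation rate of 30.9% in women aged 35 or over in an earlier phase 3 trial.
- K, the number of single transfers available to a woman. The documents give no distribution, so K is assumed. Protocol 3.5.2 says only that most women who return have 2-3 cryopreserved cycles.
- Transfers continue until success or until K is used up.

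**Formulas at constant p.**
- Per-woman mean = sum over k = 1..K of p(1-p)^(k-1)/k. For large K this tends to -p ln(p)/(1-p).
- Pooled ratio = expected fetuses / expected blastocysts = [1-(1-p)^K] / [sum over k = 1..K of (1-p)^(k-1)] = p, because the denominator equals [1-(1-p)^K]/p.

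**Example, K = 2, 100 women.** 31 succeed first (score 1). Of the other 69, 69 × 0.31 = 21.39 succeed second (score 1/2). The per-woman mean is (31 + 21.39/2)/100 = 41.7%. Pooled, it is (31 + 21.39)/(100 + 69) = 52.39/169 = 31.0%.

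| K for every woman | Per-woman mean | Pooled |
|---|---|---|
| 1 | 31.0% | 31.0% |
| 2 | 41.7% | 31.0% |
| 3 | 46.6% | 31.0% |
| 4 | 49.2% | 31.0% |
| no limit | 52.6% | 31.0% |

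| Assumed mix of K | Per-woman mean | Pooled |
|---|---|---|
| K = 1/2/3: 70/20/10 | 34.7% | 31.0% |
| 60/25/15 | 36.0% | 31.0% |
| 50/30/20 | 37.3% | 31.0% |
| equal thirds | 39.8% | 31.0% |
| 30/30/40 | 40.5% | 31.0% |
| K = 1 to 4, equal | 42.1% | 31.0% |

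**Departures from the simple model** (simulation of 400,000 women, starting from equal thirds):
- Double transfers in 20% or 40% of transfers where two blastocysts remain: 38.2% or 36.8%. If every such transfer is double: 32.7%.
- Only 70% or 50% returning after a failure: 36.7% or 35.1%.
- p varying between women (beta distribution with mean 0.31, concentration 10, 5 or 2): per-woman mean 39.0%, 38.2% or 36.6%; pooled 29.7%, 28.6% or 26.3%.
- No stopping at success: per-woman mean 31.0%. Stopping is therefore the cause.

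**The rank test.** Let p = 0.31 in both groups, with up to 3 single transfers in group A and 1 in group B. Scores in A are 1 (31.0%), 1/2 (0.69 × 0.31 = 21.4%), 1/3 (0.69² × 0.31 = 14.8%) and 0 (0.69³ = 32.9%). Scores in B are 1 (31.0%) and 0 (69.0%).
- P(A > B) = 0.69 × (1 - 0.329) = 0.463.
- P(tie) = 0.31² + 0.69 × 0.329 = 0.323.
- Concordance = 0.463 + 0.323/2 = 0.62.

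It would be 0.50 if the test responded only to the chance per blastocyst, which is identical here.

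**The case against.** **The SAP does not state a mean of per-woman ratios.** A reader might infer that the plan prescribes it. It does not: 9.4.3 names no level, although 9.4.11 to 9.4.13 do name oocyte, embryo and subject levels, and the table shells are in a separate document (SAP section 15). The programmed rate might be pooled. This stands as a limit on the claim. It does not remove the point, because the stated rank test needs a per-woman value in any case. If the rate is pooled, the test does not test the rate reported.

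**A single figure is not supported.** A reader might conclude that a 31% chance per blastocyst will be reported as about 40%. That needs equal thirds with 1, 2 or 3 available transfers, single transfers throughout and full return after failure. The plan allows double transfers when no good-quality blastocyst exists, and SAP 9.2.2 expects some women not to return. The 30.9% also comes from a trial of women aged 18-40 with a different dosing approach. Only the conditional range can be defended.

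**The pooled ratio is not every woman's chance.** This is correct when p varies between women. It is then the rate per blastocyst actually transferred, which is what SAP 2.2 describes.

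**The consequences are limited.** SAP 9.2.1 makes these endpoints supportive. A reader might expect spurious subgroup differences, but SAP 9.3.2 plans subgroup displays only for the primary endpoint. The rank test is planned only as applicable, and the placebo arm has 50 women. SAP 9.4.1 and 9.4.17 already tabulate viable fetuses and total blastocysts transferred, so the ingredients of a pooled ongoing rate are available. No pooled rate or interval is planned, however.

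**Conclusion.** The point holds in conditional form. On the natural reading of SAP 9.4.3, a mean of cumulative per-woman ratios lies above fetuses per blastocyst transferred at constant p whenever some women can have more than one transfer. The Wilcoxon test on those ratios can also show a difference between arms that differ only in blastocyst supply.

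At a constant 31% the illustration gives about 35-42% for the mixes tried, within limits of 31% and 53%, against a pooled 31%. If the chance varies between women, the pooled ratio was about 26-30% in simulation. These sizes rest on an assumed number of available transfers and on a borrowed chance per blastocyst. They apply to ongoing implantation. For gestational sacs the size will differ, because stopping follows ongoing pregnancy and not the appearance of a sac.

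The single-cycle rows, the primary test and the live-birth hierarchy are unaffected.

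**What to change.** Amend SAP 9.4.3, and 9.4.6 by reference, for two rows of each implantation endpoint: cumulative over cryopreserved cycles, and cumulative over fresh and cryopreserved cycles.

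- Report total fetuses (or sacs) divided by total blastocysts transferred in each arm. Give a confidence interval that takes the woman as the unit, from a ratio estimator or a bootstrap over women.
- If a per-woman mean is also shown, label it as such.
- Do not use the Wilcoxon test on cumulative ratios as the comparison of implantation rates.
- Leave the single-cycle rows as they are.
- Record the change in SAP section 14, which at present declares no deviation from the protocol's planned analyses. Protocol 9.7.3.3 specifies the test.

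The cost is a paragraph of SAP text, a small program change and a declared change to a supportive test. No new data are needed. The cumulative figure is likely to be somewhat less favourable.
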